#### *Demographic characteristics*

Demographic characteristics to be summarized are:

- Age (years) derived as: (Year of informed consent - Year of birth).
- Age categories: (<50, ≥50 to <65, ≥65 to <75, ≥75 years).
- Gender (Male, Female).
- Race (White, Black or African American, Asian, American Indian or Alaska native, Native Hawaiian or other pacific islander, Multiple, Unknown).
- Ethnicity (Hispanic or Latino, Not Hispanic or Latino, Unknown).
- HbA1c (%) at screening visit.
- Randomization strata of HbA1c (≤8.5%, >8.5%) at screening (data from IRT).
- Randomization strata of metformin use (Yes, No) at screening (data from IRT).
- Mean SBP at screening.
- Randomization strata of SBP (<130 mmHg, ≥130 mmHg) at screening (data from IRT).
- Baseline body mass index (BMI) (kg/m^2) derived as: (Weight in kg)/(Height in meters).
- Baseline BMI categories (<30, ≥30 kg/m^2).
- Country.

***Disease characteristics at screening or baseline***

Disease history includes:

- Duration of diabetes (years) derived as: (Date of informed consent – Date of diagnosis of diabetes + 1)/365.25.
- Duration of diabetes categories: (<10, ≥10 years).
- Age at diagnosis of diabetes (years): (Year of diagnosis of diabetes – Year of birth).
- Metformin use at screening (Yes, No).
- Duration of metformin treatment (for those patients who used metformin at screening) (years): (date of informed consent - date of first intake of metformin +1)/365.25.
- Daily dose of metformin (mg) at baseline (for those patients who used metformin at screening).
- Categorized daily dose of metformin at baseline for those patients who used metformin at screening (<1500, ≥ 1500 to <2500, ≥2500 mg).
- Duration of sulfonylurea treatment (years): (date of informed consent - date of first intake of sulfonylurea +1)/365.25.
- Sulfonylurea at screening by international nonproprietary name (INN) and formulation.
- Daily dose of sulfonylurea at baseline by INN and formulation.
- Categorized daily dose of sulfonylurea at baseline by INN:
  - Glibenclamide (Gd) and Glibenclamide MR (GdMR):
    - <10 mg/day (Gd) or <6 mg/day (GdMR),
    - ≥10 - ≤20 mg/day (Gd) or ≥6 - ≤12 mg/day (GdMR),
    - >20 mg/day (Gd) or >12 mg/day (GdMR).
  - Gliclazide (Gz) and Gliclazide MR (GzMR):
    - <160 mg/day (Gz) or <60 mg/day (GzMR),
    - ≥160 - ≤320 mg/day (Gz) or ≥60 - ≤120 mg/day (GzMR),
    - >320 mg/day (Gz) or >120 mg/day (GzMR).
  - Glimepiride:
    - <4 mg/day,
    - ≥4 - ≤8 mg/day,
    - >8 mg/day.
  - Glipizide (Gp) and Glipizide XL (GpXL):
    - <20 mg/day (Gp) or <10 mg/day (GpXL),
    - ≥20 - ≤40 mg/day (Gp) or ≥10 - ≤20 mg/day (GpXL),

- >40 mg/day (Gp) or >20 mg/day (GpXL).
- Gliquidone:
  - <90 mg/day,
  - $\geq 90 - \leq 180$  mg/day,
  - >180 mg/day.
- Baseline diabetic microvascular complications (Yes, No) (ie, diabetic retinopathy, diabetic neuropathy, diabetic nephropathy, diabetic peripheral neuropathy (sensory or motor), diabetic autonomic neuropathy, and diabetic foot infection).
- eGFR at screening (mL/min/1.73m^2).
- eGFR categories at screening (<15 mL/min/1.73m^2 [End stage renal disease],  $\geq 15$  to <30 mL/min/1.73m^2 [Severe decrease in GFR],  $\geq 30$  to <60 mL/min/1.73m^2 [Moderate decrease in GFR],  $\geq 60$  to <90 mL/min/1.73m^2 [Mild decrease in GFR], and  $\geq 90$  mL/min/1.73m^2 [Normal]).
- Prior antihypertensive medication identified by therapeutic class as agents acting on the renin-angiotensin system, beta blocking agents, diuretics (a sub-category: loop diuretics identified by pharmacological class as high-ceiling diuretics), calcium channel blockers, and antihypertensives according to World Health Organization-Drug Dictionary (WHO-DD).

### ***Medical or surgical history***

Medical history and medical findings include:

- Physical examination.
- Medical or surgical history.
- Medical history cardiovascular.
- Surgical history amputation.
- Alcohol habits.
- Tobacco smoking habits.

Medical and surgical history will be coded to a “lower level term (LLT)”, “preferred term (PT)”, “high level term (HLT)”, “high level group term (HLGT)”, and associated primary “system organ class (SOC)” using the version of Medical Dictionary for Regulatory Activities (MedDRA) currently in effect at **Covance** at the time of database lock.

Any technical details related to computation, dates, and imputations for missing dates are described in [Section 2.5](#).

### 2.1.2 Prior or concomitant medications

All medications taken within 3 months before the screening visit (any time for prior SGLT2) and until the end of the study are to be reported in the electronic case report form (e-CRF).

All medications will be coded using the World Health Organization-Drug Dictionary WHO-DD using the version currently in effect at **Covance** at the time of database lock.

- Prior medications are those the patient used prior to first administration of the double-blind IMP. Prior medications can be discontinued before first administration or can be ongoing during treatment phase.
- Concomitant medications are any treatments received by the patient concomitantly to the IMP, from the 1st administration of double-blind IMP to the date of last administration + 10 days. A given medication can be classified both as a prior medication and as a concomitant medication.
- Posttreatment medications are those the patient took in the period running from the 11th day after the last administration of double-blind IMP up to the end of the study.

Background sulfonylurea and metformin are considered as noninvestigational medicinal products (NIMP). Sulfonylurea and metformin (commercial formulations) will be administered orally according to the locally approved label.

Any technical details related to computation, dates, imputation for missing dates are described in [Section 2.5](#).

#### 2.1.2.1 Rescue therapy

Except for SGLT2 inhibitors and additional metformin and sulfonylurea, any approved medication(s) including oral antidiabetic drugs, GLP-1 receptor agonists, or insulin can be prescribed at the Investigator's discretion to treat the hyperglycemia. Metformin will also be permitted for patients on sulfonylurea only at Screening. Rescue therapy is considered a NIMP.

#### 2.1.2.2 Prohibited prior and concomitant medications

During the study treatment period, the following medications are prohibited:

- Initiation of any antidiabetic agents, including oral or injectable antihyperglycemic agents other than the IMP before the rescue therapy.  
Note: short term use (<10 consecutive days) of the prohibited medication, eg, short-acting insulin for treatment of acute illness or surgery is allowed.
- Systemic use of glucocorticoids for more than 10 consecutive days (topical, ophthalmic, nasal spray or inhaled applications are allowed).
- Initiation of any weight loss drugs (eg, phentermine, orlistat).

- Investigational medicinal products in any other clinical study.

SGLT2 inhibitors (eg, canagliflozin, dapagliflozin, or empagliflozin), additional sulfonylurea and metformin are not allowed for rescue or post IMP therapy until the end of study.

Reduction of digoxin dose should be considered because sotagliflozin acts as a weak P-glycoprotein inhibitor and increases systemic exposure to digoxin.

Other medications which are unlikely to interfere with the pharmacokinetic (PK) or pharmacodynamic (PD) of the IMP or confound interpretation of the study endpoints are allowed as needed following discussion between the Investigator and the Sponsor. However, doses of chronically administered medicines should be kept fixed during the trial if at all possible.

After premature permanent discontinuation of the IMPs, any treatments (other than SGLT2 inhibitors) are permitted, as deemed necessary by the Investigator.

The dose of all antihypertensive agents should be kept constant during the 12 weeks following randomization and no antihypertensive agents should be added or withdrawn for the 12 weeks following randomization unless it is considered necessary for safety reasons.

### 2.1.3 Efficacy endpoints

All efficacy measurements collected during the study will be considered for analyses, including those obtained after IMP discontinuation or introduction of rescue therapy (see [Section 2.5.4](#)).

HbA1c, FPG, serum creatinine, eGFR are measured/calculated in a central laboratory (see study flowchart in [D](#)). Body weight, SBP and diastolic blood pressure (DBP) (see [Section 2.1.4.5](#)) are measured at on-site visits by the investigator. Patients requiring rescue are identified as those with the reason for treatment ticked “rescue therapy” in e-CRF “Medication” page.

Efficacy variables will be summarized in both standard international units and conventional units when applicable.

#### 2.1.3.1 Primary efficacy endpoint(s)

- Change from Baseline to Week 26 in HbA1c (%).

#### 2.1.3.2 Secondary efficacy endpoint(s)

- Change from Baseline to Week 26 in FPG.
- Change from Baseline to Week 26 in body weight.
- Change from Baseline to Week 12 in SBP for patients with baseline SBP  $\geq$ 130 mmHg.
- Change from Baseline to Week 12 in SBP for all patients.
- Proportion of patients with HbA1c <6.5%, <7.0% at Week 26.

### 2.1.3.3 Other efficacy endpoint(s)

- Change from Baseline to Week 12 in SBP for patients with baseline SBP <130 mmHg.
- Proportion of patients with reduction in body weight by  $\geq 2\%$ ,  $\geq 5\%$ , and  $\geq 10\%$  from Baseline.
- Change from Baseline to Week 12 in DBP.
- Proportion of patients achieving SBP <130 mmHg for those with baseline SBP  $\geq 130$  mmHg.
- Proportion of patients achieving DBP <80 mmHg for those with baseline DBP  $\geq 80$  mmHg.
- Proportion of patients requiring rescue for hyperglycemia.
- Change from Baseline in:
  - Serum creatinine,
  - eGFR.
- Change from Baseline to Week 79 in HbA1c.
- Change from Baseline to Week 79 in FP.
- Change from Baseline to Week 26 in SBP for all patients and for patients with baseline SBP  $\geq 130$  mmHg.
- Change from Baseline to Week 79 in SBP for all patients and for patients with baseline SBP  $\geq 130$  mmHg.
- Change from Baseline to Week 79 in body weight.

### 2.1.4 Safety endpoints

The safety analysis will be based on the reported adverse events (AEs), hypoglycemia, and other safety information, such as clinical laboratory data, vital signs, electrocardiogram (ECG), and physical examination, etc.

#### *Observation period*

The observation period will be divided into 4 epochs:

- The **screening** epoch is defined as the time from the signed informed consent date up to the first administration of the double-blind IMP.
- The **treatment** epoch is defined as the time from the first administration of the double-blind IMP to the last administration of the double-blind IMP. This epoch includes the 26-week double-blind core treatment period and the 53-week double-blind extension treatment period. The core treatment period is the time from the first administration of double-blind IMP to the last administration of double-blind IMP on or before Visit 9/Week 26 (or Day 182 if Visit 9/Week 26 date is missing).

- The **residual treatment** epoch is defined as the time from the last administration of the double-blind IMP up to 10 days (1 day for hypoglycemia) after the last administration of double-blind IMP.

The treatment-emergent adverse event (TEAE) period will include both treatment and residual treatment epochs (See the TEAE period for the core treatment period in [Section 2.5.4](#)).

- The **posttreatment** epoch is defined as the period of time starting the day after the end of the TEAE period up to the last protocol-planned visit or the resolution/stabilization of all serious adverse events (SAE), adverse events of special interest (AESI) and events of special interest (EOSI), whichever is later.

The on-study observation period is defined as the time from start of double-blind treatment until the end of the study (defined as the last scheduled visit for those who completed the study and the date collected on e-CRF page “Completion of End of Study/Follow-up” for those who did not complete the study).

The post-study observation period is defined as the time from the day after the end of the study until the resolution/stabilization of all SAE, AESI and EOSI if applicable.

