### **2.4.5 Analyses of safety data**

The summary of safety results will be presented by treatment group.

Safety endpoints are presented in [Section 2.1.4](#). The summary of safety results will be presented by treatment group. The safety data will be summarized for the 26-week core treatment period and the 79-week entire treatment period separately, unless otherwise specified.

The “observation period” defined in [Section 2.1.4](#) is applicable in all safety analyses for the classification of AEs, determination of treatment-emergent PCSA values and the last on-treatment value for the laboratory, vital sign and ECG.

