#### **2.4.5.1 Analyses of hypoglycemia**

Analyses of hypoglycemia will be performed on the TEAE periods as defined in [Section 2.1.4](#). Hypoglycemia will be classified as severe hypoglycemia, documented symptomatic hypoglycemia, asymptomatic hypoglycemia, probable symptomatic hypoglycemia or relative hypoglycemia [Section 2.1.4.1](#).

The number (%) of patients with any hypoglycemia, severe hypoglycemia, and documented symptomatic hypoglycemia will be summarized respectively by treatment group during the TEAE period, as well as the incidence rate in patient years. Two types of incidence rates will be presented: the number of patients with at least 1 event per 100 patient years (calculated as the number of patients with at least 1 event / total exposure in 100 patient years), and the number of events per 100 patient-years [calculated as the total number of events / (total exposure in 100 patient-years)]. Note: here exposure (in days) is duration of TEAE period, ie, duration of IMP treatment in days +1 (Section 2.1.4).

The summary of frequency and incidence rate in patient years for severe hypoglycemia or documented symptomatic hypoglycemia will be provided as appropriate by gender (Male, Female), age group (<50, ≥50 to <65, ≥65 years), race (White, Black or African American, Asian, Other) and Metformin use at Screening (Yes, No).

A KM curve will also be provided by treatment group for the time to first severe hypoglycemia or documented symptomatic hypoglycemia during the TEAE period for the 79-week entire treatment period only.

Documented symptomatic hypoglycemia maybe presented by  $\leq 3.9$  mmol/L ( $\leq 70$  mg/dL) and  $< 3.0$  mmol/L ( $< 54$  mg/dL) respectively, as appropriate.

A listing of patients for all events reported on the dedicated e-CRF “Hypoglycemic event information” page will be provided with each category flagged (ie, severe hypoglycemia, documented symptomatic hypoglycemia, asymptomatic hypoglycemia, probable symptomatic hypoglycemia and relative hypoglycemia).

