#### **2.4.5.2 Analyses of adverse events**

##### **Generalities**

The primary focus of adverse event reporting will be on TEAEs. Pretreatment and posttreatment AEs will be described separately.

If an AE date/time of onset (occurrence, worsening, or becoming serious) is incomplete, an imputation algorithm will be used to classify the adverse event as pretreatment, treatment-emergent, or posttreatment. The algorithm for imputing date/time of onset will be conservative and will classify an AE as treatment emergent unless there is definitive information to determine it is pretreatment or posttreatment. Details on classification of AEs with missing or partial onset dates are provided in Section 2.5.3.

Adverse event incidence tables will be presented by SOC, HLG, HLT, and PT, sorted by the internationally agreed order for SOCs and alphabetic order for HLG, HLT and PT within a SOC, the number (n) and percentage (%) of patients experiencing an adverse event. Multiple occurrences of the same event in the same patient will be counted only once in the tables within a treatment phase. The denominator for computation of percentages is the safety population within each treatment group.

Sorting within tables ensures the same presentation for the set of all AEs within the observation period (pretreatment, treatment-emergent, and posttreatment). For that purpose, the table of all TEAEs presented by primary SOC and PT (sorted by the internationally agreed SOC order and decreasing frequency of PTs within SOCs in the sotagliflozin 400 mg group) will define the presentation order for all other similar tables unless otherwise specified. In case of equal frequency regarding PTs, alphabetical order will be used.

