#### **Analysis of EOSI**

The summaries of EOSI will be presented for the 79-week entire treatment period only in the safety population.

*CV events, bone fracture and DKA*

For EOSIs that are adjudicated (ie, deaths, myocardial infarction, stroke, and unstable angina requiring hospitalization, heart failure requiring hospitalization, bone fracture, and diabetic ketoacidosis), the number (%) of patients with an EOSI positively adjudicated by CEC will be summarized by treatment group. All EOSIs sent for adjudication and/or reported by the investigators in the specific AE forms will be listed along with the adjudication outcome.

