#### *Other EOSIs*

For EOSIs that are not adjudicated, the number (%) of patients with at least one event will be summarized by treatment group and by PT (as identified in [Table 3](#) in [Section 2.1.4.2](#)).

Severe hypoglycemia will be included in the summary of hypoglycemia (See [Section 2.5.1](#)).

AE leading to an amputation is described in the section below.

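### Most events of special interest are reported over 79 weeks only as crude percentages, although each patient's time at risk ends 10 days after the last dose (minor; cheap to improve)

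*SAP*

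**What the plan says.** **Window.** In the SAP's Observation period text (2.1.4), "The treatment-emergent adverse event (TEAE) period will include both treatment and residual treatment epochs". The residual epoch runs "up to 10 days (1 day for hypoglycemia) after the last administration of double-blind IMP". SAP 2.4.5 states that this observation period "is applicable in all safety analyses for the classification of AEs".

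**Measure.** In the Generalities of SAP 2.4.5.2, "The denominator for computation of percentages is the safety population within each treatment group". For EOSIs, "The summaries of EOSI will be presented for the 79-week entire treatment period only in the safety population". Within that period:
- For adjudicated events other than renal, "the number (%) of patients with an EOSI positively adjudicated by CEC will be summarized by treatment group".
- Renal events get a number and percentage by arm.
- For non-adjudicated events, "the number (%) of patients with at least one event will be summarized by treatment group and by PT".
- The general safety rules in 2.4.5 allow relative risks versus placebo with 95% CIs if relevant. They mention no exposure adjustment.

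**Exceptions.**
- Severe hypoglycaemia is an EOSI but is reported with hypoglycaemia in 2.4.5.1, where "Two types of incidence rates will be presented", both per 100 patient-years.
- Amputation procedures are counted whether on or after treatment (Analysis of Amputation).
- Deaths are also tabulated on-study (2.4.5.3).

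Cumulative exposure in patient-years is planned by arm (2.4.3.1) but is not used as a denominator for any other EOSI.

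**The concern.** The window differs between patients. Someone who stops at Week 4 is observed for treatment-emergent events for about 5 weeks and a completer for about 80 weeks, yet each counts as one unit in the denominator. The percentage therefore combines the event rate with the time on drug. If one arm stops more, or stops earlier, its percentage falls with no difference in the underlying rate.

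This matters most for EOSIs that accumulate with time, such as fractures, urinary tract infections and cardiovascular events. Their grouped tables exist only for the 79-week period, where exposure can differ most between arms. Assessing safety against placebo throughout 79 weeks is a stated secondary objective (protocol 5.2, SAP 1.2.2).

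**Working it through.** The documents state no event rate, discontinuation rate or expected exposure, so there is no figure of the plan's own to reproduce on this point. The check asks what the crude percentages show when the true rate is identical in both arms.

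**Inputs from the documents**
- Treatment length T = 79 weeks = 553 days = 1.514 years.
- Residual window r = 10 days = 0.0274 years.
- 250 patients per arm (SAP 1.3).

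**Assumptions**
- Constant event rate λ = 0.05 per year in both arms.
- A proportion d stops drug by T, with exponential time to stopping at rate θ = −ln(1 − d)/T.
- Stopping is unrelated to event risk.

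**Formula.** Time at risk is W = min(stopping time, T) + r. The expected crude proportion is

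P = 1 − E[exp(−λW)] = 1 − exp(−λr) × [θ + λ exp(−(θ+λ)T)] / (θ+λ).

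**Worked case, 10% versus 30% stopped**
- d = 10%: θ = 0.0696, exp(−0.1196 × 1.514) = 0.834, P = 1 − 0.9986 × (0.0696 + 0.05 × 0.834)/0.1196 = 7.05%.
- d = 30%: θ = 0.2356, exp(−0.2856 × 1.514) = 0.649, P = 1 − 0.9986 × (0.2356 + 0.05 × 0.649)/0.2856 = 6.27%.
- Crude ratio = 7.05/6.27 = 1.12; the true ratio is 1.00.

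| Stopped by Week 79 | Crude % | Patients of 250 | Crude ratio | Mean time at risk, W (years) |
|---|---|---|---|---|
| 10% vs 10% | 7.05 vs 7.05 | 17.6 vs 17.6 | 1.00 | 1.464 vs 1.464 |
| 15% vs 20% | 6.86 vs 6.67 | 17.2 vs 16.7 | 1.03 | 1.425 vs 1.384 |
| 15% vs 25% | 6.86 vs 6.48 | 17.2 vs 16.2 | 1.06 | 1.425 vs 1.343 |
| 10% vs 30% | 7.05 vs 6.27 | 17.6 vs 15.7 | 1.12 | 1.464 vs 1.301 |

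The crude ratio is close to the ratio of mean time at risk (1.464/1.301 = 1.13 in the last row). At 10 and 20 per 100 patient-years the ratios are almost the same.

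**Masked excess.** Solving P for λ at 30% stopping so that it equals 7.05% gives a rate about 13% above 0.05. An excess of that size in the arm that stops more would not show.

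**Timing alone.** Let 20% stop in each arm, at Day 30 in one and Day 400 in the other. P = 0.2 × [1 − exp(−λ(day + 10)/365.25)] + 0.8 × [1 − exp(−λ × 563/365.25)], which is 6.04% and 7.03%, ratio 0.86. Equal totals stopped do not guarantee a fair comparison.

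**Does the remedy work?** Mean time to first event or end of window is P/λ, that is 1.410 and 1.255 years in the 10%/30% case. The first-event rates are 0.0705/1.410 and 0.0627/1.255, both 5.0 per 100 patient-years, ratio 1.00.

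**Against sampling error.** With 17.6 and 15.7 events of 250, SE(log ratio) = √(1/17.6 − 1/250 + 1/15.7 − 1/250) = 0.335. The 95% CI around 1.12 is exp(0.117 ± 1.96 × 0.335), about 0.58 to 2.2.

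**The case against.** **The plan is not blind to unequal exposure.** It reports exposure by arm in categories and in patient-years (SAP 2.4.3.1), Kaplan-Meier plots of discontinuation for any reason and for adverse events (2.2), and post-treatment adverse events in their own table (2.4.5.2). A reader could see an imbalance and judge its rough effect. This stands and lowers the weight of the point, but it leaves the correction to the reader.

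**EOSIs are not confined to 79 weeks in every form.** Those defined by preferred terms also appear, term by term, in the 26-week TEAE tables. This stands; only the grouped rows lack a 26-week version.

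**Safety is descriptive, and the imbalance is assumed.** No tests are planned, rescued patients stay on study drug (protocol 8.2.2), and permanent discontinuation is a last resort (protocol 10.3). All of this stands, as does the comparison with sampling error. It bears on size, not on the mechanism.

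**The window is inferred for EOSIs.** The EOSI text does not itself restate last dose plus 10 days; the limit comes from SAP 2.1.4 read with 2.4.5. For renal events that need at least 30 days of confirmation or 90 days of dialysis (SAP Table 3), how it applies is unclear.

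**Person-time rates have limits too.** If patients stop because of factors linked to event risk, a rate censored at the end of the window is also biased; and a patient who stops because of an event has already been counted. This stands.

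A reader might infer that every TEAE and EOSI comparison is distorted, or that risks of sotagliflozin will be understated. The documents support neither: the three exceptions fall outside the point, and no rate or direction of differential stopping is given.

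**Conclusion.** The point holds in limited form. Outside the three exceptions, the grouped 79-week EOSI tables offer no measure that separates event rate from time on drug, although the SAP already provides one for hypoglycaemia. Under the assumed stopping patterns the crude ratio is 1.03 to 1.12 when the true ratio is 1.00, and about 0.86 in the deliberately extreme timing example. These figures rest on constant hazards, stopping unrelated to event risk, and stopping rates that are not in the documents. Crude percentages remain valid as description, and the primary HbA1c conclusion is untouched. This is a minor point, worth acting on because it is cheap.

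**What to change.** In SAP 2.4.5.2, for the grouped 79-week EOSI tables, add beside the number and percentage:
- the number of patients with a first event per 100 patient-years at risk, with time at risk running to the first event or, if there is none, to the end of the TEAE period in 2.1.4;
- the between-arm rate difference with 95% CI, labelled as descriptive.

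The same rate could be added to the TEAE overview if wanted. Extending rate differences to all common-TEAE tables goes further than needed. State which window applies to renal events.

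The cost is SAP wording and programming, since the dates are already collected. There are two downsides. The rate assumes a roughly constant hazard and stopping unrelated to event risk, so the crude percentage should stay alongside it. It also differs from the hypoglycaemia convention, which divides by total exposure rather than time to first event, so a footnote should say so.
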